9.1.1 Definition of cycles

The e-Diary entries will be assigned to cycles in the following way.

The duration of cycle -2 is based on the menstruation dates log at visit 1 and visit 2. The date of the first day that belongs to cycle -2 is the start date of menses in the current cycle from visit 1 +7 days (note that if visit 1 is performed before this date there will be e-Diaries not assigned to a cycle, and if visit 1 is performed after this date there will be days in cycle -2 without an e-Diary). The last day that belongs to cycle -2 is the start date of menses in the current cycle from visit 2 +6 days.

The duration of the other cycles are defined in a similar way. The duration of cycle -1 is based on the menstruation dates log at visit 2 and visit 4. The duration of cycle 1 is based on the menstruation dates log at visit 4 and end-of-cycle 1 visit , and equivalently for cycle 2 to 10. If the start date of menses in the current cycle is missing at a visit, due to that the subject did not have menstrual bleeding just prior to that visit (the RM+7 visit in a cycle must be arranged within 35 days of the last RM+7 visit regardless of the subject has had menses). Then the two cycles from the RM+7 of previous, cycle to RM+7 of next cycle will be divided in two equally long cycles. E.g. if start date of menses in the current cycle is missing at end-of-cycle 2 visit (due to that the subject did not report menses), then cycle 2 will end and cycle 3 begin half way between start date of menses in the current cycle from end-of-cycle 1 visit and end-of-cycle 3 plus 7 days.

If the start date of menses in the current cycle in the menstruation log is missing for any other reason than the one mentioned above. Then the first date in that cycle where the subject answers yes to both question 9 and 11 in the e-Diary will be used instead.

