# 3.6.5 Selection and Timing of Dose for Each Subject

In this clinical trial, the duration of treatment is based on individual subject's menstrual cycle length rather than calendar time points, matching the visits and timings of evaluation with the replacement of the vaginal ring. A menstrual cycle is considered the period between day 7 of return of menses (RM+7) in a cycle until the following day 7 of return of menses of the next cycle. Visits on RM+7 can be scheduled day 6 to day 10 day of return of menses (RM+6-10).

Subjects will be instructed to insert the assigned ring in the upper part of the vagina at RM+7 visits, a timing that corresponds to the stop of menstrual bleeding and is convenient for administration of a vaginal product, which can therefore easily be remembered and followed by subjects. The vaginal ring will be kept in the vagina continuously for one menstrual cycle until being replaced by the next

ring on RM+7 of the next cycle when the subject visits the clinic. Thus, quinagolide will be given sufficient time to inhibit the endometriotic lesions prior to return of the menses in the next cycle, when the majority of the most severe endometriosis-related pain occurs.

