#### 6.1 Activities between Clinic Visits

In this trial, a menstrual cycle is considered the period between day 7 of return of menses (RM+7) in a cycle until the following RM+7. Visits on RM+7 can be scheduled on RM+6-10, i.e. day 6 to day 10 of return of menses. Similarly, visits on LH+7 can be scheduled on LH+6-9, i.e. 6-9 days after LH surge, which is either assessed by the subject using LH surge kits at home or estimated by the site staff based on subject's cycle length. If subjects do not have menstrual bleeding in a cycle during the treatment and follow-up period, the RM+7 visit in that cycle must be arranged within 35 days of the last RM+7 visit.

The review of the e-Diary, which covers compliance with e-Diary completion and analgesic use should be performed by site staff regularly between clinic visits.

Contraception counselling and condoms will be offered to subjects as needed throughout the trial.

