10.1 General Considerations

Safety parameters will be evaluated for the safety analysis data set.

All safety summaries will be performed by treatment:

For adverse events (AE) and concomitant medications the following rules will apply;

Treatment period	AE and concomitant medications to be included
Part A	Start after start of IMP, and start date before or equal to the date of the end-of-cycle 4 visit, if missing use date of premature discontinuation
Part B	Start date after the date of the end-of-cycle 4visit and before or equal to date last ring removal, if missing use date of premature discontinuation.

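### When menses is absent at the end-of-cycle-4 visit, the SAP closes cycle 4 at a calendar midpoint, not the recorded ring date, so a few off-drug or post-switch days can enter the primary score

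*SAP*

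**What the plan says.** SAP 9.1.1 builds each cycle from the menses start dates confirmed at the RM+7 visits, with the boundary a fixed number of days after menses starts. If a start date is missing because the woman did not bleed, the two cycles between the neighbouring RM+7 dates "will be divided in two equally long cycles". The SAP's example concerns the end-of-cycle-2 visit: "then cycle 2 will end and cycle 3 begin half way between start date of menses in the current cycle" recorded at the visits on either side, shifted by 7 days. The cycle rules run "and equivalently for cycle 2 to 10", so they cover the end of cycle 4.

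The visit takes place even without menses. SAP 9.1.1 says that "the RM+7 visit in a cycle must be arranged within 35 days of the last RM+7 visit regardless of the subject has had menses". Protocol 6.1 says, only for cycles without bleeding, that "the RM+7 visit in that cycle must be arranged within 35 days of the last RM+7 visit".

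Rings are changed or removed at these visits. Protocol 7.4.18 records the date and time, and SAP 8.1.1 uses those dates for exposure. Protocol 3.6.5 describes the design as "matching the visits and timings of evaluation with the replacement of the vaginal ring". For adverse events, SAP 10.1 closes Part A with "start date before or equal to the date of the end-of-cycle 4 visit".

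After the end-of-cycle-4 visit, a version 6.0 woman has no ring (Protocol 6.4.6 and 6.5). In the Part A/Part B design, placebo women move to quinagolide and active-arm women keep their dose (SAP section 3). SAP 9.1.4.1 still scores a cycle without menses, as a simple mean, provided no more than half of its daily scores are missing.

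**The concern.** The primary endpoint is the change in the cycle 4 mean. The date on which treatment ends or switches is known for every woman who attends the end-of-cycle-4 visit, but the midpoint rule ignores it. The diary continues after that visit, so later scores exist that can be counted in cycle 4. Neither document cuts the cycle 4 diary at ring removal or at the start of Part B.

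If the midpoint falls after the visit, two groups are affected. Version 6.0 active-arm women contribute off-drug days, and Part A/Part B placebo women contribute quinagolide days. With an effective drug, both would pull the reported difference from placebo towards zero. If the midpoint falls before the visit, on-treatment days move out of cycle 4.

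The rule also needs a later menses date. If menses is absent at the following visit too, or no later date can be had from the log or the diary, cycle 4 has no defined end.

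**Working it through.** The plan gives no figure for misassigned days, and the sample-size calculation does not enter this point. The check is date arithmetic.

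**Inputs**
- Day 0 is the RM+7 date ending cycle 3. I assume that visit took place on RM+7 itself.
- v is the day of the end-of-cycle-4 visit, held without menses.
- D is the day of the next RM+7 date based on menses.
- Boundary = D/2 (SAP 9.1.1).
- Visit window: "Visits on RM+7 can be scheduled on RM+6-10, i.e. day 6 to day 10 of return of menses" (Protocol 6.1). The earliest valid visit is therefore one day before RM+7.

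Days after the visit that count in cycle 4 = D/2 − v. This is accurate to about one day, depending on how the evening entry on the visit day is treated.

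**Largest excess under the SAP's visit limit.** The next visit is due by day v + 35. If it falls on RM+6, the latest RM+7 date is D = v + 36, and the excess is (v + 36)/2 − v = (36 − v)/2.

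| v | Latest D | Boundary = cycle 4 length | Days after the visit | Share of cycle 4 |
|---|---|---|---|---|
| 35 | 71 | 35.5 | 0.5 | 1.4% |
| 28 | 64 | 32 | 4 | 12.5% |
| 24 | 60 | 30 | 6 | 20% |

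**Under the protocol's wording.** The limit binds only when there is no bleeding, so menses may start as late as day v + 35. Then D = v + 35 + 6 = v + 41 and the excess is (41 − v)/2. At v = 28 this is 6.5 days of 34.5 (19%), or 7.5 if the visit-day entry is counted: about 7.

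**Opposite direction.** With v = 35:
- D = 49: 24.5 − 35 = −10.5 days.
- D = 56: 28 − 35 = −7 days.

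Here cycle 4 is shortened, but every day kept is on treatment.

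**Illustrative size on the NRS.** Assume that the full 1.0-unit design effect appears or vanishes at once. An affected woman's cycle 4 mean then moves by the share: 0.125 at v = 28 and 0.20 at v = 24. The documents give no rate of absent menses. If 5% to 20% of a group were affected:
- v = 28: 0.125 × 0.05 = 0.006 to 0.125 × 0.20 = 0.025 units on the group mean.
- v = 24: 0.20 × 0.05 = 0.01 to 0.20 × 0.20 = 0.04 units.

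**After the change.** With the boundary at the ring date, D/2 is replaced by v and the excess is 0, again to within the visit-day entry.

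**The case against.** Several objections have force.

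- **Size.** A reader might infer contamination of a week even for a visit on day 35, for example with the next RM+7 on day 84. The visit limit rules that out. Menses would have to start on day 78, 43 days after the visit, but a no-menses visit would already have been due by day 70. The start date would be missing again and the rule would not run. A no-menses visit near the 35-day limit gives half a day at most under the SAP's wording.
- **Scope.** A reader might infer that every affected woman has mixed treatment. She does not. Part A/Part B active-arm women keep their dose, and version 6.0 placebo women only lose a placebo ring. Absent menses at an earlier visit moves a boundary within one treatment.
- **Remedy.** A reader might want the ring date used at every boundary. Suppose menses is absent at the end of cycle 3, the ring is changed on day 35 and the next RM+7 is day 49. Cycle 4 would then last 14 days and include the menses. Assuming 5 menstrual days, they would make up 5/14 = 36% of it, against 5/24.5 = 20% under the equal split. The equal split is sensible there.
- **Status.** Protocol 9.6.1 leaves cycle definitions to the SAP, so this is not a protocol breach. Even with menses present the boundary follows menses rather than the ring visit, although then at most about one post-removal day enters. The adverse-event rule in SAP 10.1 serves a different purpose, so its use of the visit date is not in itself a contradiction.
- **Consequence.** SAP sections 1 and 12 drop all statistical analysis. A reader might infer a loss of power or a distorted test, but no test will be run.

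These objections limit the point without removing it. At the end of cycle 4 the rule can still admit days under a different treatment, and it can fail to give a boundary although the visit date is on file.

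**Conclusion.** The weakness is real but small. It arises only when menses is absent at the end-of-cycle-4 visit. It mixes treatments only when the midpoint falls after that visit, and only for version 6.0 active-arm women and Part A/Part B placebo women. The excess is at most about 0.5, 4 or 6 days for a visit on day 35, 28 or 24 under the SAP's visit limit, and about 7 days on day 28 under the protocol's wording. These figures assume an end-of-cycle-3 visit on RM+7 and are accurate to about one day.

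Few women should be affected: eligibility requires two run-in cycles of 24 to 35 days (Protocol 4.1.1), and Protocol 3.6.2 does not expect quinagolide to change bleeding. With descriptive reporting, only the cycle 4 summaries can move. Because few subjects were recruited, each affected woman weighs more in those summaries.

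**What to change.** Add to SAP 9.1.1: when menses is absent at the end-of-cycle-4 visit, cycle 4 ends on the recorded date of ring removal or change at that visit, and no later diary day counts towards cycle 4. List the women to whom this applies. Keep the equal split at the other boundaries, where treatment does not change.

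This also gives cycle 4 an end when the next menses date is missing. It does not supply the cycle 3/4 boundary if menses is absent at both the end-of-cycle-3 and end-of-cycle-4 visits, so a further sentence could cover that case. The SAP and Protocol 6.1 wordings of the 35-day limit should also be reconciled.

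The cost is a sentence or two and one listing. The dates are already collected and already used for exposure, so this is a free improvement.

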9.1.2 Definition of menstrual period and non-menstrual period

Each cycle is divided into a menstrual period and a non-menstrual period, unless the subject does not have a menstrual bleeding during that cycle (see section 9.1.1), then the entire cycle will be considered non-menstrual.

The first day of menses is based on the start date of menses in the current cycle from the menstruation dates log. If this is missing for any other reason than the subject did not have menses in this cycle, then the first day in that cycle where the subject answers yes to both question 9 and 11 in the e-Diary will be used instead.

The last day of menses is based on the stop date of menses in the current cycle from the menstruation dates log. If the subject does have menses and the stop date is missing then the first day where the subject answers no to either question 9 or 11 in the e-Diary will be used instead. Note that the last day of menses could be in the next cycle relative to the first day of menses.

The menstrual period is defined as the period from the first day of menses to the last day of menses, both included.

The menstrual period of a cycle consists of the bleeding period in the end of the cycle plus the potential bleeding part in the beginning of the cycle. If a subject does not bleed in the end of the cycle, the entire cycles will be considered non-menstrual.

The non-menstrual part of the cycle is defined as the part of the cycle that is not considered the menstrual part.

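### SAP 9.1.1/9.1.2: the diary fallback for a missing menses start date can take the tail of the previous period as the next onset, which cuts that woman's cycle 4 to 7 days

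*SAP*

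**What the plan says.** SAP 9.1.1 starts cycle -2 at "the start date of menses in the current cycle from visit 1 +7 days". It ends that cycle as follows: "The last day that belongs to cycle -2 is the start date of menses in the current cycle from visit 2 +6 days". For the rest, "The duration of the other cycles are defined in a similar way", so cycle 4 follows the same rule. The protocol counts the start date as day 1 of menses, so the first day of a cycle is bleeding day 8.

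The SAP gives two rules for a missing start date. If there was no menstrual bleeding, the two adjoining cycles are split equally. If the date "is missing for any other reason than the one mentioned above", the diary is used: "the first date in that cycle where the subject answers yes to both question 9 and 11 in the e-Diary will be used instead". Question 9 asks about any vaginal bleeding and question 11 asks whether it was menstrual. SAP 9.1.2 repeats the fallback for the first day of menses: "then the first day in that cycle where the subject answers yes to both question 9 and 11 in the e-Diary".

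That section also expects bleeding to cross the cycle boundary: "Note that the last day of menses could be in the next cycle relative to the first day of menses". It counts bleeding at the beginning of a cycle as part of that cycle's menstrual period. Protocol 5.1.1 likewise has the ring inserted at RM+7 whether or not bleeding has stopped.

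**The concern.** The fallback is meant to find the next onset of menses. It sets no earliest day, no exclusion of the preceding bleed and no minimum cycle length. The phrase about that cycle gives no end to the search, because the end is what the missing date should supply. The beginning is fixed, however, so a continuing bleed on cycle day 1 lies inside the search window and comes first.

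The cycle 4 score is the primary endpoint. A cut-off cycle loses the days before the next menses and the first week of that menses, which is when protocol 3.6.5 expects most of the worst pain. The lost days move into the following cycle. The same error at a run-in visit would distort baseline.

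The completeness rules do not catch it. The 50% rule in SAP 9.1.4.1 and the per-protocol exclusion for more than 20% missing diary days in SAP 5 are both judged against the derived cycle. A fully recorded 7-day cycle passes both.

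**Working it through.** The plan states no figure on this point to reproduce, so the check is date arithmetic on the literal rule.

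**Inputs.** From SAP 9.1.1: first cycle day = start + 7; last cycle day = next start + 6; fallback start = first day in the cycle with yes to questions 9 and 11. From the protocol's inclusion criterion 11: true cycle length of 24 to 35 days. The NRS profiles below are assumptions and come from no document.

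**1. Rule with the date logged.** Let S be the logged start at the end-of-cycle-3 visit and L the true cycle length. Cycle 4 runs from S+7 to S+L+6, which is L days: 24, 28 or 35, as it should be.

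**2. Date missing, preceding period of 7 days or less.** The first yes/yes day is S+L, the true onset. The cycle length is again 24, 28 or 35 days, so the fallback works.

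**3. Date missing, bleeding day 8 reported as menstrual.** The first yes/yes day is S+7. The last cycle day is S+7+6 = S+13, so the length is 13 − 7 + 1 = 7 days. That is 7/24 = 29%, 7/28 = 25% or 7/35 = 20% of the true cycle. Between 24 − 7 = 17 and 35 − 7 = 28 days fall outside cycle 4. If day 8 is answered no and day 9 yes, the cycle is 8 days.

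**4. Completeness.** Take an 8-day period whose stop date comes from the diary. SAP 9.1.2 takes the first no day as the last day of menses, so the 7 days split into 2 menstrual and 5 non-menstrual. Half of each, rounded up, is 1 + 3 = 4 diary entries. Four entries are enough for a cycle 4 score.

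**5. Effect on one woman's cycle 4 score** (28-day cycle, 8-day menses, complete diary, so the length-weighted mean equals the simple mean). The true cycle has 1 day at bleeding day 8, 20 other days and 7 menses days. The cut-off cycle has bleeding day 8 and 6 other days.

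- Menses days 8, day 8 scored 5, other days 4: true (5 + 20×4 + 7×8)/28 = 141/28 = 5.04; fallback (5 + 6×4)/7 = 29/7 = 4.14; error −0.89.
- Menses days 6, otherwise the same: true (5 + 80 + 42)/28 = 127/28 = 4.54; fallback 4.14; error −0.39.

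**6. End-of-cycle-3 date missing instead.** Cycle 3 becomes 7 days and cycle 4 takes over its other 21 days: 21 + 28 = 49 days. On the 8/5/4 profile these are 14 days at 8, one at 5 and 34 at 4: (112 + 5 + 136)/49 = 253/49 = 5.16, against 5.04. The error is +0.13, small and in the opposite direction.

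**7. Effect on a group mean.** One affected woman among n shifts the mean by her error divided by n. At the planned 52 evaluable per group, 0.89/52 = 0.017. The documents do not give the actual group sizes, only that few subjects were recruited.

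**The case against.** The best defence is that the fallback replaces a start date, and SAP 9.1.2 defines each menses from its first to its last day. A day that belongs to the previous menses is then not a start, and a sensible programmer would skip it. That is probably the intent, but it is not what the text instructs, and two programmers could derive different cycle 4 scores from it.

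Several limits do stand.

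- The error needs two events in the same woman: a start date absent although she menstruated, and menstrual bleeding reported on cycle day 1. Protocol 7.4.7 has staff confirm the start date at every RM+7 visit, and protocol 3.6.5 chose that timing because bleeding has usually stopped. The documents give no frequency for either event.
- The SAP performs no statistical or interim analysis, so no test or stopping decision is affected.

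Three stronger inferences are tempting and are not supported.

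- A reader might set 0.89 beside the planned effect of 1.0. The first is one hypothetical woman's error; the second is a difference between group means.
- A reader might assume that the COVID-19 hold caused many lost dates. Protocol 9.3 plans listings of missed visits and assessments, but does not say that menses dates were lost. A woman without an end-of-cycle-4 visit is not counted as completing Part A (SAP 8.1.1).
- A reader might conclude that the cycle 4 score is badly wrong whichever date is missing. In step 6 the shift is small.

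**Conclusion.** Wrong as written, with low to moderate severity. The 7-day result follows exactly from the literal rule whenever the start date is missing despite menses and the preceding period is reported as menstrual on bleeding day 8. Protocol 9.6.1 gives a diary fallback only for the last bleeding date. It leaves cycle conventions to the SAP, so the start-date rule is the SAP's own to get right.

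For an affected woman the cycle 4 score falls by roughly 0.4 to 0.9 points when the end-of-cycle-4 date is missing, and rises by about 0.13 (8/5/4 profile) when the end-of-cycle-3 date is missing. These sizes rest on assumed pain profiles, a 28-day cycle, an 8-day menses and complete diaries. The apparent improvement depends on menses days being worse than other days. The number of women affected is unknown. The consequence is confined to their scores and to the descriptive summaries, where one wrong value weighs more in a small group.

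**What to change.** In SAP 9.1.1 and 9.1.2, replace the fallback with wording to this effect: use the first day with yes to both question 9 and question 11 after the previous menses has ended. The end is its logged stop date or, if that is missing, the first completed diary entry after its onset answering no to question 9 or 11. Search up to the next RM+7 visit or the next logged start date. Missing diary days do not count as non-bleeding days.

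The diary branch matters because protocol 7.4.7 records a stop date only if menses has finished by the visit, so long bleeders will often lack one.

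If no such day is found in a woman who did menstruate, flag the cycle for blinded data review or set its score to missing. Do not apply the no-menses split, which is reserved for women without bleeding. A single no entry within a long bleed could still mislead the search, so also flag for review any fallback-derived cycle outside 24 to 35 days.

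The cost is a few sentences of SAP text, slightly more derivation code and possibly a few more missing cycle scores.

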9.1.2 Definition of menstrual period and non-menstrual period

Each cycle is divided into a menstrual period and a non-menstrual period, unless the subject does not have a menstrual bleeding during that cycle (see section 9.1.1), then the entire cycle will be considered non-menstrual.

The first day of menses is based on the start date of menses in the current cycle from the menstruation dates log. If this is missing for any other reason than the subject did not have menses in this cycle, then the first day in that cycle where the subject answers yes to both question 9 and 11 in the e-Diary will be used instead.

The last day of menses is based on the stop date of menses in the current cycle from the menstruation dates log. If the subject does have menses and the stop date is missing then the first day where the subject answers no to either question 9 or 11 in the e-Diary will be used instead. Note that the last day of menses could be in the next cycle relative to the first day of menses.

The menstrual period is defined as the period from the first day of menses to the last day of menses, both included.

The menstrual period of a cycle consists of the bleeding period in the end of the cycle plus the potential bleeding part in the beginning of the cycle. If a subject does not bleed in the end of the cycle, the entire cycles will be considered non-menstrual.

The non-menstrual part of the cycle is defined as the part of the cycle that is not considered the menstrual part.

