## 7.4.7 Menstruation Dates

At each RM+7 visit throughout the trial, the site staff should confirm the subject's start date of menses in the current cycle, i.e. the first menstrual bleeding date (RM+1). If the subject has finished her menses when coming to the visit, the site staff should also confirm the stop date of menses in the current cycle, i.e. the last menstrual bleeding date.

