### **Missing Data**

## Missing data for endometriosis-related pain

If a subject has indicated that too much pain is the reason for not completing the diary on some day, the missing data for that day will be derived by taking a worst-case approach, i.e. assigning an NRS of 10 for endometriosis-related pain. Otherwise the score remains to be missing.

As endometriosis-related pain is potentially different during the menstrual-bleedings days from during the non-menstrual-bleeding days, at least 50% of the NRS scores are required to be observed for both the menstrual period and the non-menstrual period to be able to calculate the mean daily NRS score for a particular cycle. As missing NRS scores may not be appropriately balanced across menstrual period and non-menstrual period, the mean daily NRS score based on observed data will be weighted by the lengths of the menstrual period and non-menstrual period to adjust for this potential imbalance.

So the mean daily NRS score is calculated as

$$\frac{l_{mp}\overline{x}_{mp} + l_{non-mp}\overline{x}_{non-mp}}{l_{mp} + l_{non-mp}}$$

Where  $l_{mp}$  is the length of the observed menstrual period,  $l_{non-mp}$  is the length of the observed non-menstrual period,  $\bar{x}_{mp}$  is the mean daily NRS score based on observed NRS scores during the menstrual period, and  $\bar{x}_{non-mp}$  is the mean daily NRS score based on observed NRS scores during the non-menstrual period.

The observed cycle length will be based on the first menstrual bleeding date confirmed at the RM+7 visit of each cycle (section 7.4.7). The length of the observed menstrual period will be based on the first and last menstrual bleeding dates confirmed at the RM+7 visit of each cycle. If the last menstrual bleeding date cannot be confirmed at the RM+7 visit (section 7.4.7), the date of the last reported menstrual bleeding day recorded in the e-Diary will be used. The length of the observed non-menstrual period will be calculated as the observed cycle length minus the length of the observed menstrual period.

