9.1.4.1 The mean daily NRS score for worst endometriosis related pain

For each cycle, at least 50% of the NRS scores are required to be observed (including the imputed values as described in subsection 9.1.3) for both the menstrual period and the non-menstrual period (as defined in subsection 9.1.2) to be allowed to calculate the mean daily NRS score for that particular cycle. So if above 50% of the daily NRS scores are missing in either period of that cycle, the mean daily NRS score for worst endometriosis related pain for that cycle should be missing.

As missing daily NRS scores may not be appropriately balanced across menstrual period and non-menstrual period, the mean daily NRS score will be weighted by the lengths of the menstrual period and non-menstrual period to adjust for this potential imbalance.

So the mean daily NRS score is calculated as

$$\frac{l_{mp}\overline{x}_{mp} + l_{non-mp}\overline{x}_{non-mp}}{l_{mp} + l_{non-mp}}$$

Where l_{mp} is the number of days in the menstrual period of the cycle (as defined in subsection 9.1.2), l_{non-mp} is the number of days in the non-menstrual period of the cycle in question (as defined in subsection 9.1.2), \bar{x}_{mp} is the mean daily NRS score based on the observed daily NRS scores (question 1) during the menstrual period (including imputations as described in 9.1.3), and \bar{x}_{non-mp} is the mean daily NRS score (question 1) based on the observed daily NRS scores during the non-menstrual period (including imputations as described in 9.1.3).

If the subject does not have a menstrual period in a cycle the mean daily score is calculated as a simple mean, however if more than 50% of the daily NRS scores are missing the mean daily NRS will be considered missing

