9.1.4.2 The mean daily NRS score for worst dysmenorrhea

For each cycle the mean daily NRS score for worst dysmenorrhea is defined as the mean daily NRS score for worst endometriosis related pain (question 1) during the menstrual period of that cycle (as defined in subsection 9.1.2).

If above 50% of the daily NRS scores in the menstrual period of a cycle are missing, the mean daily NRS score for worst dysmenorrhea for that cycle should be missing.

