9.1.6 Responder status

Twelve different definitions of responder status are being used in this trial, one for each combination of the 4 mean daily NRS score defined in section 9.1.4 and the 3 thresholds \geq 30%, \geq 50% and \geq 70%.

A subject is defined as being a responder in a specific cycle if the mean daily NRS score is reduced with at least the threshold value compared to baseline and that the percentage of days on any analgesics has not increased by more than 10% since baseline.

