9.1.8 Vaginal bleeding pattern

The vaginal bleeding pattern is evaluated as the number of days per cycle with no bleeding, spotting, light bleeding, moderate bleeding and heavy bleeding days, respectively. Additionally the duration of menstrual and non-menstrual period, and the number of bleeding days during the non-menstrual period, will be calculated.

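### When the logged stop date of menses is missing, SAP 9.1.2 ends menses on the first day reported as non-menstrual and counts that day as menstrual

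*SAP*

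**What the plan says.** SAP 9.1.2 takes the start and stop of menses from the menstruation dates log. For a woman who had menses but has no logged stop date, the rule is: "stop date is missing then the first day where the subject answers no to either question 9 or 11 in the e-Diary will be used". The menstrual period is then "the period from the first day of menses to the last day of menses, both included".

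Question 9 asks about any vaginal bleeding in the past 24 hours. Question 11 asks whether that bleeding was menstrual. A 'no' to either means no menstrual bleeding over the same 24 hours as that entry's pain score.

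Protocol 9.6.1, under the missing-data rules for endometriosis-related pain, covers the same situation differently: "the date of the last reported menstrual bleeding day recorded in the e-Diary will be used". Protocol 7.4.7 describes what sites log as "the stop date of menses in the current cycle, i.e. the last menstrual bleeding date".

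The period feeds several outputs:
- the dysmenorrhea and non-menstrual pelvic pain means (SAP 9.1.4.2 and 9.1.4.3)
- responder status, which asks "if the mean daily NRS score is reduced with at least the threshold value compared to baseline" (SAP 9.1.6)
- the bleeding-pattern summaries, including "the duration of menstrual and non-menstrual period, and the number of bleeding days during the non-menstrual period" (SAP 9.1.8)
- the weights and the 50% completeness rule for the primary mean (SAP 9.1.4.1).

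**The concern.** The substituted day is, by the woman's own report, not a day of menstrual bleeding, yet it is counted as one. This conflicts with protocol 9.6.1 and with the meaning of the logged stop date. It also conflicts with the SAP itself, which describes dysmenorrhea as pain on days with menstrual bleeding (sections 2.5 and 3) and whose fallback for a missing start date uses a day with 'yes' to both questions. Women with a logged date and women on the fallback are summarised together under different definitions of menses.

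The fallback is foreseeable. Sites confirm the stop date only if menses has finished by the visit, which may fall on day 6 to day 10 of menses, and protocol 5.1.1 allows for women who are still bleeding then.

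At stake are the dysmenorrhea and non-menstrual pain summaries, their responder rates and the recorded length of menses. Because no inferential analysis is planned, these summaries are the trial's efficacy output.

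**Working it through.** The documents give no figure on this point, so the sizes below are illustrations.

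**Inputs.** From the SAP: cycle *k* ends on the start date of menses + 6 days, which is menses day 7 (9.1.1), and the weighted mean is that of 9.1.4.1. Assumed: a 28-day cycle, menses of *L* = 6 days, menstrual pain *m*, non-menstrual pain *n*, gap *g* = *m* − *n* of 1 to 3 points, and pain on the first 'no' day equal to *n*.

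**When the fallback applies.** Visit days in 6–10 on which menses is unfinished: *L* = 5, none; *L* = 6, day 6; *L* = 7, days 6 and 7; *L* = 8, days 6 to 8.

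**Last day of menses under each rule** (Y = menstrual, N = not, . = no entry):

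| Diary from day 1 | SAP 9.1.2 | Protocol 9.6.1 |
|---|---|---|
| YYYYYYNNNN | 7 | 6 |
| YYYNYYYNNN | 4 | 7 |
| YYYYYY..NN | 9 | 6 |
| YYYYY.NNNN | 7 | 5 |

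Unbroken menses is one day too long. One isolated 'no' cuts it short, and the later bleeding days become non-menstrual.

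**Dysmenorrhea mean, complete diaries.** Shift = (*Lm* + *n*)/(*L* + 1) − *m* = −*g*/(*L* + 1). For *L* = 6: −1/7 = −0.14 to −3/7 = −0.43. The added day 7 lies in the same cycle.

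**Primary mean, complete diaries.** [7 × (6*m* + *n*)/7 + 21*n*]/28 = (6*m* + 22*n*)/28. This equals the value under the protocol rule, so the shift is 0.

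**Change from baseline in dysmenorrhea.**
- Fallback in every cycle, gap 3 at baseline and 1 at cycle 4: (−1/7) − (−3/7) = +0.29, so the recorded improvement is 0.29 too small.
- Fallback at cycle 4 only: −*g*/7, so the improvement is 0.14 to 0.43 too large.
- The shifts cancel only if the gap and the menses length are the same at both times.

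**Responder example.** Baseline dysmenorrhea 7.0 from logged dates; at cycle 4, dysmenorrhea 5.0 and non-menstrual pain 3.0. True reduction: (7 − 5)/7 = 28.6%. With the fallback at cycle 4 the mean is (6 × 5 + 3)/7 = 4.71, and the reduction is (7 − 4.714)/7 = 32.7%. The woman becomes a 30% responder, if the analgesic condition is met.

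**Primary mean, missing diaries.**
- Three of six menstrual entries missing, day 7 answered 'no': [7 × (3*m* + *n*)/4 + 21*n*]/28 − (6*m* + 22*n*)/28 = −0.75*g*/28, or −0.03 to −0.08. With *m* = 7 and *n* = 4, 4.643 becomes 4.5625.
- Day 7 missing, first 'no' on day 8: (7*m* + 21*n*)/28 − (6*m* + 22*n*)/28 = *g*/28, or +0.04 to +0.11.

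**50% rule.** The cycle mean is set to missing "if above 50% of the daily NRS scores are missing in either period of that cycle". Suppose days 2–4 and 7 are missing, day 6 is 'yes' to both, and the first 'no' is on day 8. The protocol rule gives 3/6 = 50% missing and the mean is calculated. The SAP rule gives 4/7 = 57% missing and the primary mean for that cycle is lost.

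**The case against.** - **The extra day often falls in the next cycle.** This stands. A cycle ends on menses day 7, so for *L* of 7 or more the first 'no' day belongs to the following cycle, and that cycle's dysmenorrhea mean moves instead (*L* = 7 in both cycles: −*g*/8, or 0.13 to 0.38 for gaps of 1 to 3). If the stop date is missing because menses is unfinished at the visit that closes cycle 4, the cycle 4 and responder examples need a 6-day menses and a day-6 visit. With longer menses, a stop date missing at the end of cycle 3 is what disturbs cycle 4.
- **Pain may taper.** If pain on the first 'no' day lies between *m* and *n*, the dysmenorrhea shift is smaller and the non-menstrual mean moves a little. The unchanged primary mean with complete diaries does not depend on this.
- **With day 7 missing, nobody knows whether it was menstrual.** This also stands. The +0.04 to +0.11 and the 4/7 example show that the two rules disagree, not that the SAP must be the one in error.
- **Logged spans can also contain a 'no' day.** True, since both documents use a start-to-stop span. But a logged span ends on a bleeding day, and the fallback span does not.
- **Protocol 9.6.1 leaves cycle and menses conventions to the SAP.** It does, but it also states this particular rule, and the SAP gives no reason for changing it.
- **Version.** SAP section 1 makes protocol 5.0 the basis for the report, and only 6.0 is available here. The departure from 9.6.1, and its absence from SAP section 12, can be judged only against 6.0. The inconsistency within the SAP does not depend on the version.

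**Conclusion.** The concern holds and is minor. As written, the fallback labels a day reported as non-menstrual as the last day of menses, and an isolated 'no' can instead end menses too early. Per affected cycle, under the assumptions above, menses is one day too long and the dysmenorrhea mean is 0.14 to 0.43 too low. With complete diaries the primary mean is unaffected. With missing diaries it moves by about 0.1 or less in either direction, or drops out under the 50% rule. The number of affected cycles cannot be worked out from the documents. With descriptive reporting only, the harm is mislabelled summaries, not a wrong test.

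**What to change.** In SAP 9.1.2, when the stop date is missing, take the last e-Diary day of that menses with 'yes' to both Question 9 and Question 11, in line with protocol 9.6.1. Because an isolated 'no' should not end menses, it would help to add a few words on what separates one menses from later bleeding; neither document says. If the present rule is intended, list it in SAP section 12 as a departure and give the reason.

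The cost is a clause or two of text and a small programming change, with no new data. If outputs already exist, the tables that use the menstrual period need a rerun.
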